### 7.2.2 Severity of AEs

All non-hematologic adverse events will be graded according to the NCI Common Terminology Criteria for Adverse Events (CTCAE) version 4.03. The CTCAE v4.03 is available at <http://ctep.cancer.gov/reporting/ctc.html>

If no CTCAE grading is available, the severity of an AE is graded as follows:

- Mild (grade 1): the event causes discomfort without disruption of normal daily activities.
- Moderate (grade 2): the event causes discomfort that affects normal daily activities.
- Severe (grade 3): the event makes the patient unable to perform normal daily activities or significantly affects his/her clinical status.
- Life-threatening (grade 4): the patient was at risk of death at the time of the event.
- Fatal (grade 5): the event caused death.

### 7.2.3 Serious Adverse Events (SAEs)

All SAEs, regardless of attribution, occurring from time of signed informed consent, through 30 days after the last administration of study drug, must be reported upon discovery or occurrence.

An SAE is defined in regulatory terminology as any untoward medical occurrence that:

- **Results in death.**  
If death results from (progression of) the disease, the disease should be reported as event (SAE) itself.
- **Is immediately life-threatening.**  
The patient was at risk of death at the time of the event; it does not refer to an event that hypothetically might have caused death if it were more severe.
- **Requires *in-patient hospitalization or prolongation of existing hospitalization for ≥ 24 hours.***
- **Results in persistent or significant disability or incapacity.**
- **Is a congenital anomaly/birth defect.**
- **Is an important medical event.**

Any event that does not meet the above criteria, but that in the judgment of the investigator jeopardizes the patient, may be considered for reporting as a serious adverse event. The event may require medical or surgical intervention to prevent one of the outcomes listed in the definition of "Serious Adverse Event".

For example: allergic bronchospasm requiring intensive treatment in an emergency room or at home; convulsions that may not result in hospitalization; development of drug abuse or drug dependency.

The causality of SAEs (their relationship to all study treatment/procedures) will be assessed by the investigator(s) and communicated to AstraZeneca.

### 7.2.4 Exceptions to AE and SAE definitions

Generally speaking, any adverse event that results in hospitalization or prolonged hospitalization should be documented and reported as an SAE, as described above. Likewise, any condition responsible for surgery should be documented as an AE if the condition meets the criteria for an AE. However, for the purposes of this study, neither the condition, hospitalization, prolonged hospitalization, nor surgery are reported as AEs or SAEs under the following circumstances:

- Hospitalization or prolonged hospitalization is for a diagnostic or elective surgical procedure for a preexisting condition. Surgery should not be reported as an outcome of an adverse event if the purpose of the surgery was elective or diagnostic and the outcome was uneventful.
- Hospitalization or prolonged hospitalization is required to allow efficacy measurement for the study.
- Hospitalization or prolonged hospitalization is required for study-directed therapy of the target disease of the study, unless it is a worsening or increase in frequency of hospital admissions as judged by the principal investigator.
- Hospitalization or prolonged hospitalization is due to social reasons (i.e. awaiting transport home).
- Pregnancy is not considered a serious adverse event, any patients who become pregnant during the study should discontinue the study immediately. Patients should be instructed to notify the investigator if it is determined after completion of the study that they become pregnant either during the treatment phase of the study or within 30 days or five half-lives after the treatment period, whichever is longer.

### 7.2.5 Durvalumab & Tremelimumab Adverse Events of Special Interest (AESI)

An adverse event of special interest (AESI) is one of scientific and medical interest specific to understanding of the Investigational Product and may require close monitoring and rapid communication by the investigator to the sponsor. An AESI may be serious or non-serious. The rapid reporting of AESIs allows ongoing surveillance of these events in order to characterize and understand them in association with the use of this investigational product.

AESIs for durvalumab ± tremelimumab include but are not limited to events with a potential inflammatory or immune-mediated mechanism and which may require more frequent monitoring and/or interventions such as steroids, immunosuppressants and/or hormone replacement therapy. These AESIs are being closely monitored in clinical studies with durvalumab monotherapy and combination therapy. An immune-mediated adverse event (imAE) is defined as an AESI that is associated with drug exposure and is consistent with an immune-mediated mechanism of action and where there is no clear alternate etiology. Serologic, immunologic, and histologic (biopsy) data, as appropriate, should be used to support an imAE diagnosis. Appropriate efforts should be made to rule out neoplastic, infectious, metabolic, toxin, or other etiologic causes of the imAE.

If the Investigator has any questions in regards to an event being an imAE, the Investigator should promptly contact the Study Physician.

AESIs observed with durvalumab ± tremelimumab include but are not limited to:

- Diarrhea/Colitis
- Intestinal perforation
- Pneumonitis
- ALT/AST increases/hepatitis/hepatotoxicity
- Neuropathy/neuromuscular toxicity (eg. Guillain-Barré syndrome, and myasthenia gravis)
- Myositis/polymyositis
- Endocrinopathies (ie, events of hypophysitis/hypopituitarism, adrenal insufficiency, and hyper- and hypothyroidism, Type I diabetes mellitus)
- Rash/Dermatitis
- Myocarditis
- Nephritis
- Pancreatitis (or labs suggestive of pancreatitis - increased serum lipase, increased serum amylase)
- Other inflammatory responses that are rare with a potential immune-mediated etiology are also considered as AESIs and include, but are not limited to, pericarditis, sarcoidosis, and uveitis and other events involving the eye, skin, hematological and rheumatological events. It is possible that events with an inflammatory or immune mediated mechanism could occur in nearly all organs.

The following are more details on specific AESIs:

#### **7.2.5.1 Pneumonitis**

Across the durvalumab monotherapy pooled dataset pneumonitis events observed (pneumonitis, ILD, acute interstitial pneumonitis and pulmonary fibrosis) were reported at a frequency rate of Common (98/1889; 5.2%).

Adverse events of pneumonitis are also of interest for AstraZeneca, as pneumonitis has been observed with anti-PD-1 and anti-PD-L1 mAbs (but not with anti-PD-L1 mAbs). Initial work-up should include high-resolution CT scan, ruling out infection, and pulse oximetry. Pulmonary consultation is highly recommended. Presentations of pneumonitis can range from asymptomatic lung infiltrates to those that mimic

severe bacterial pneumonia [40]. Early consideration of pneumonitis should be realised when patients present with new onset or worsening of respiratory symptoms such as dyspnea or cough. Prompt treatment with steroids is important as per current established toxicity management guidelines.

Guidelines for the management of patients with immune-related AEs (irAEs) including pneumonitis are provided in Table 1.

#### **7.2.5.2 Infusion reactions**

AEs of infusion reactions (also termed infusion-related reactions) are of special interest to AstraZeneca and are defined, for the purpose of this protocol, as all AEs occurring from the start of IP infusion up to 48 hours after the infusion start time. For all infusion reactions, SAEs should be reported to AstraZeneca Patient safety as described in Section 10.3.

#### **7.2.5.3 Hypersensitivity reactions**

Hypersensitivity reactions as well as infusion-related reactions have been reported with anti-PD-L1 and anti-PD-1 therapy (Brahmer et al 2012). As with the administration of any foreign protein and/or other biologic agents, reactions following the infusion of mAbs can be caused by various mechanisms, including acute anaphylactic (IgE-mediated) and anaphylactoid reactions against the mAbs and serum sickness. Acute allergic reactions may occur, may be severe, and may result in death. Acute allergic reactions may include hypotension, dyspnea, cyanosis, respiratory failure, urticaria, pruritus, angioedema, hypotonia, arthralgia, bronchospasm, wheeze, cough, dizziness, fatigue, headache, hypertension, myalgia, vomiting, and unresponsiveness. Guidelines for the management of patients with hypersensitivity (including anaphylactic reaction) and infusion-related reactions are provided in Table 1.

#### **7.2.5.4 Hepatic Function Abnormality**

Hepatic function abnormality is defined as any increase in ALT or AST to greater than  $3 \times$  ULN and concurrent increase in bilirubin to greater than  $2 \times$  ULN. Examples of hepatitis abnormality are autoimmune hepatitis, hepatitis toxic, hepatocellular injury, hepatotoxicity resulting in hyperbilirubinemia. Concurrent findings are those that derive from a single blood draw or from separate blood draws taken within 8 days of each other. Follow-up investigations and inquiries will be initiated promptly by the investigational site to determine whether the findings are reproducible and/or whether there is objective evidence that clearly supports causation by a disease (eg, cholelithiasis and bile duct obstruction with distended gallbladder) or an agent other than the investigational product. Guidelines for management of patients with hepatic function abnormality are provided in Table 1.

#### **7.2.5.5 Gastrointestinal disorders**

**Diarrhea/colitis:** is the most commonly observed treatment emergent SAE when tremelimumab is used as monotherapy, but may also be related to durvalumab. In rare cases, colon perforation may occur that requires surgery (colectomy) or can lead to a fatal outcome if not properly managed. There were no CTC Grade 4 or 5 events from the pooled dataset, however, fatal events of colitis have been reported with durvalumab in combination with tremelimumab. Guidelines on management of diarrhea and colitis in patients receiving tremelimumab are provided in Table 1.

##### **➤ Intestinal perforation**

Across the durvalumab monotherapy pool of studies, intestinal perforation was reported at a frequency rate of Uncommon (2/1889; 0.1%); CTCAE Grades 2 and 4. There were no Grade 5 events.

In the durvalumab + tremelimumab combination pooled dataset, intestinal perforation was reported in 3/1088 patients (0.3%); Uncommon and large intestine perforation was reported in

4 patients (0.4%; Uncommon). All events were CTCAE Grade 4 or 5 in severity. One patient from study D4190C00010 died due to the event of intestinal perforation and had concurrent peritonitis/Grade 4 sepsis; autopsy was not performed. Another patient died due to the event of large intestine perforation and disease progression (Study D4190C00006). Both cases were not considered as treatment-related by the Investigator.

Monitor for symptoms that may be related to bowel perforation such as sepsis, peritoneal signs, and ileus (refer to the Toxicity Management Guidelines for diarrhoea/colitis). Investigators should adhere to the overall management for immune-mediated toxicities by performing a thorough evaluation to rule out alternative aetiologies and by initiating prompt treatment including steroids.

#### **7.2.5.6 Endocrine disorders**

Immune-mediated endocrinopathies include hypophysitis, adrenal insufficiency, and hyper- and hypothyroidism. Guidelines for the management of patients with immune-mediated endocrine events are provided in Table 1.

#### **7.2.5.7 Pancreatic disorders**

Immune-mediated pancreatitis includes autoimmune pancreatitis, and lipase and amylase elevation. Pancreatitis is an inflammatory condition of the pancreas that typically manifests initially as asymptomatic elevations of amylase and lipase in patients treated with immune checkpoint inhibitors. Across the 1889 patients in the monotherapy program, events of pancreatitis were Uncommon to rare. Four patients (0.2%) experienced pancreatitis (CTC Grade 2, Grade 3 and Grade 4 in severity) and 1 patient (<0.1%) with CTC Grade 3 acute pancreatitis. Elevations in amylase and lipase were reported at a frequency rate of Uncommon (0.6% and 0.5%, respectively). In ongoing sponsored studies with durvalumab + tremelimumab therapy in 1088 patients, events of pancreatitis were Uncommon; pancreatitis was reported in 10 patients (0.9%) with 5 of these CTC Grade 3 in severity. Elevations in amylase and lipase were reported at a frequency of Common (91 patients; 8.4% and 101 patients; 9.3%, respectively). Most events of amylase increased were Grades 1 and 2 in severity while events of lipase increased tended to be more severe (Grade 3 and Grade 4) with the combination. Patients should be monitored for signs and symptoms of pancreatitis including Grade 3 or 4 elevations in lipase and/or amylase. Close monitoring, early detection and prompt treatment of these events are important.

Guidelines for the management of patients with immune-mediated pancreatic disorders are provided in Table 1.

#### **7.2.5.8 Neurotoxicity**

Immune-mediated nervous system events include encephalitis, peripheral motor and sensory neuropathies, Guillain-Barré, and myasthenia gravis. Guidelines for the management of patients with immune-mediated neurotoxic events are provided in Table 1.

#### **Myositis/polymyositis**

In the durvalumab pool of studies as of the DCO, 3 patients (0.2%) reported the event of myositis, including 1 CTCAE Grade 3 in severity. Outside of the pooled dataset, there were 2 fatal events of polymyositis considered as treatment-related by the Investigator.

In the durvalumab + tremelimumab combination pool, Grade 3 myositis event were reported in 1 patient (<0.1%). In addition, there were 4 SAEs of myositis reported from studies outside of the pooled dataset. Grade 2 polymyositis was reported in 1 patient (<0.1%) from the combination pooled dataset and 2 additional patients (1 each retrieved from the global safety database and a study outside of the pooled dataset). The severity of these events were Grade 3 and Grade 5 with the latter patient having died due to the event of polymyositis which was considered related by the Investigator. Autopsy showed polymyositis involving the diaphragm and chest wall muscles.

Investigators should adhere to the Toxicity Management Guidelines by performing a thorough evaluation to rule out alternative aetiologies and initiating prompt treatment with steroids and modification of study drug dose regimen depending on the severity of the event. Refer to the Toxicity Management Guidelines.

#### **7.2.5.9 Nephritis**

Immune-mediated renal events include nephritis. Management of patients with immune-related nephritis are provided in Table 1.

#### **7.2.5.10 Dermatitis**

Immune-mediated rashes can occur such as dermatitis. Management guidelines of immune-related dermatitis are reviewed in Table 1.

#### **Myocarditis**

Across the durvalumab monotherapy pool of studies, as of the DCO of 12 July 2017 there has been 1 serious report of CTC Grade 3 myocarditis and 2 additional cases (Grade 3 and Grade 4) outside of the pooled dataset. In all cases the patients recovered or were improving with corticosteroid therapy.

Across the durvalumab plus tremelimumab combination pool of studies as of 12 July 2017 there has been 1 report of myocarditis. In addition myocarditis has been reported in 4 patients from clinical studies outside of the pooled dataset: 3 patients receiving durvalumab plus tremelimumab (1 of which resulted in a fatal outcome not considered related by the Investigator) and 1 patient receiving durvalumab plus tremelimumab in combination with cytotoxic chemotherapy agents, etoposide and carboplatin (which resulted in a fatal outcome).

Investigators should be aware of such rare, but severe immune-mediated adverse events including myocarditis with its presenting signs/symptoms (eg, decreased ejection fraction, arrhythmias, in particular occurrences of atrioventricular block).

For patients with suspected myocarditis, investigators should obtain a cardiology consult and institute full diagnostic work-up (that includes exclusion of other alternate causes such as infection) and the appropriate management that includes discontinuing drug (permanently if event progresses to Grade 3 or 4) and the prompt use of steroids or other immunosuppressives.

For rapid recovery of Grade 1 and 2 events, re-expose with treatment is possible. Patients with pre-existing cardiac disorders should be closely monitored for deterioration in their cardiac condition, which could suggest new onset myocarditis.

#### **7.2.5.11 Immune-related adverse events**

Based on the mechanism of action of durvalumab and tremelimumab leading to T-cell activation and proliferation, there is a possibility of observing irAEs

during the conduct of this study. Potential irAEs may be similar to those seen with the use of ipilimumab, BMS-936558 (anti-PD-1 mAb), and BMS-936559 (anti-PD-L1 mAb) and may include immune-mediated enterocolitis, dermatitis, hepatitis (hepatotoxicity), pneumonitis, and endocrinopathies (Hodi et al 2010, Brahmer et al 2012, Topalian et al 2012). These AEs are inflammatory in nature and can affect any organ. With anti-PD-L1 and anti-CTLA-4 combination therapy, the occurrence of overlapping or increasing cumulative toxicities that include irAEs could potentially occur at higher frequencies than with either durvalumab or tremelimumab monotherapy. Patients should be monitored for signs and symptoms of irAEs. In the absence of an alternate etiology (eg, infection or PD), an immune-related etiology should be considered for signs or symptoms of enterocolitis, dermatitis, pneumonitis, hepatitis, and endocrinopathy. In addition to the dose modification guidelines provided in Table 1, it is recommended that irAEs are managed according to the general treatment guidelines outlined for ipilimumab (Weber et al 2012). These guidelines recommend the following:

- Patients should be evaluated to identify any alternative etiology.
- In the absence of a clear alternative etiology, all events of an inflammatory nature should be considered immune related.
- Symptomatic and topical therapy should be considered for low-grade events.
- Systemic corticosteroids should be considered for a persistent low-grade event or for a severe event.
- More potent immunosuppressives should be considered for events not responding to systemic steroids (eg, infliximab or mycophenolate).
- If the Investigator has any questions in regards to an AE being an irAE, the Investigator should immediately contact the treating physician.

#### **7.2.5.12 Other rare or less frequent AESIs and immune-mediated adverse events**

Events with an inflammatory or immune mediated mechanism could occur in nearly all organs.

Inflammatory events that are less frequent with a potential immune-mediated aetiology are also considered as AESIs and include, but are not limited to, pericarditis, sarcoidosis, uveitis, and other events involving the eye (eg, keratitis and optic neuritis), skin (eg, scleroderma and vitiligo), haematological (eg, haemolytic anaemia and, immune thrombocytopenic purpura) and rheumatological events (polymyalgia rheumatic and autoimmune arthritis).

#### **7.2.6 Other events requiring immediate reporting**

##### **7.2.6.1 Overdose**

An overdose is defined as a patient receiving a dose of durvalumab + tremelimumab in excess of that specified in the Investigator's Brochure, unless otherwise specified in this protocol.

Any overdose of a study patient with the durvalumab + tremelimumab, with or without associated AEs/SAEs, is required to be reported within 24 hours of knowledge of the event to the sponsor and AstraZeneca/MedImmune Patient Safety or designee using the designated Safety e-mailbox (refer section 7.3.3.4). If the overdose results in an AE, the AE must also be recorded on the AE eCRF. Overdose does not automatically make an AE serious, but if the consequences of the overdose are serious, for example death or hospitalization, the event is serious and must be reported as an SAE. There is currently no specific treatment in the event of an overdose of durvalumab or tremelimumab.

### **7.2.6.2 Pregnancy**

#### **Maternal exposure**

If a patient becomes pregnant during the course of the study, the IPs should be discontinued immediately.

Pregnancy itself is not regarded as an AE unless there is a suspicion that the IP under study may have interfered with the effectiveness of a contraceptive medication. Congenital abnormalities or birth defects and spontaneous miscarriages should be reported and handled as SAEs. Elective abortions without complications should not be handled as AEs. The outcome of all pregnancies (spontaneous miscarriage, elective termination, ectopic pregnancy, normal birth, or congenital abnormality) should be followed up and documented even if the patient was discontinued from the study.

If any pregnancy occurs in the course of the study, then the Investigator or other site personnel should inform the appropriate AstraZeneca representatives within 1 day, ie, immediately, but **no later than 24 hours** of when he or she becomes aware of it. The designated AstraZeneca representative will work with the Investigator to ensure that all relevant information is provided to the AstraZeneca Patient Safety data entry site within 1 to 5 calendar days for SAEs and within 30 days for all other pregnancies. The same timelines apply when outcome information is available.(refer section 7.3.3.4).

#### **Paternal exposure**

Male patients should refrain from fathering a child or donating sperm during the study and for 180 days after the last dose of durvalumab + tremelimumab combination therapy or 90 days after the last dose of durvalumab monotherapy, whichever is the longer time period.

Pregnancy of the patient's partner is not considered to be an AE. However, the outcome of all pregnancies (spontaneous miscarriage, elective termination, ectopic pregnancy, normal birth, or congenital abnormality) occurring from 180 days after the last dose of durvalumab + tremelimumab combination therapy or 90 days after the last dose of durvalumab monotherapy, whichever is the longer time period if possible, be followed up and documented.

Where a report of pregnancy is received, prior to obtaining information about the pregnancy, the Investigator must obtain the consent of the patient's partner. Therefore, the local study team should adopt the generic ICF template in line with local procedures and submit it to the relevant Ethics Committees (ECs)/Institutional Review Boards (IRBs) prior to use.

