**NU Study Number: NU 15B01**

**Other Study Number: MedImmune # ESR-14-10694 (D4190C00030)**

Should a female patient become pregnant or suspect she is pregnant while participating in this study, she should inform her treating physician immediately. Refer to section 4.5.1 for details.

- 3.1.14 Willingness to provide a fresh biopsy prior to study enrollment and after 2 cycles of treatment as clinically appropriate per PI discretion
- 3.1.15 Patients must have the ability to understand and the willingness to sign a written informed consent prior to registration on study. Written informed consent and HIPAA authorization will be obtained from the subject prior to performing any protocol-related procedures, including screening evaluations
- 3.1.16 Subject is willing and able to comply with the protocol for the duration of the study including undergoing treatment and scheduled visits and examinations including follow up.

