#### **4.5 Other Restrictions During the Study**

##### **4.5.1 Birth control**

The following restrictions apply while the patient is receiving study treatment and for the specified times before and after:

Female patient of child-bearing potential

- Females of childbearing potential who are sexually active with a non-sterilized male partner must use at least 1 **highly** effective method of contraception (Table 1) from the time of screening and must agree to continue using such precautions for 180 days after the last dose of durvalumab + tremelimumab combination therapy or 90 days after the last dose of durvalumab monotherapy. Non-sterilized male partners of a female patient must use male condom plus spermicide throughout this period. Cessation of birth control after this point should be discussed with a responsible physician. Not engaging in sexual activity for the total duration of the drug treatment and the drug washout period is an acceptable practice; however, periodic abstinence, the rhythm method, and the withdrawal method are not acceptable methods of birth control. Female patients should also refrain from breastfeeding throughout this period.

Male patients with a female partner of childbearing potential

- Non-sterilized males who are sexually active with a female partner of childbearing potential must use a male condom plus spermicide from screening through 180 days after receipt of the final dose of durvalumab + tremelimumab combination therapy or 90 days after receipt of the final dose of durvalumab monotherapy. Not engaging in sexual activity is an acceptable practice; however, occasional abstinence, the rhythm method, and the withdrawal method are not acceptable methods of contraception. Male patients should refrain from sperm donation throughout this period.
- Female partners (of childbearing potential) of male patients must also use a highly effective method of contraception throughout this period (Table 1).

N.B Females of childbearing potential are defined as those who are not surgically sterile (ie, bilateral tubal ligation, bilateral oophorectomy, or complete hysterectomy) or post-menopausal.

Women will be considered post-menopausal if they have been amenorrheic for 12 months without an alternative medical cause. The following age-specific requirements apply:

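### Section 7.2.6.2, read literally, follows up partner pregnancies only once the protected period has ended, and so omits those that occur during treatment and washout

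*Combined protocol and SAP*

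**What the plan says.** **Partner pregnancies.** Under Paternal exposure, Section 7.2.6.2 sets the protected period: "Male patients should refrain from fathering a child or donating sperm during the study and for 180 days after the last dose" of combination therapy, or 90 days after the last dose of monotherapy, whichever is longer. The next paragraph says that a partner's pregnancy is not an adverse event. It asks for outcome follow-up of partner pregnancies "occurring from 180 days after the last dose of durvalumab + tremelimumab combination therapy or 90 days after the last dose of durvalumab monotherapy", again whichever is longer. It gives no earlier start and no end.

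**Contraception period.** Section 4.5.1 says that female patients "must agree to continue using such precautions for 180 days after the last dose of durvalumab + tremelimumab combination therapy", or for 90 days after monotherapy, and gives male patients the same two durations. Section 3.1.13 gives 180 days after either.

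**Patient pregnancies.** Section 7.2.4 covers pregnancies identified after study completion. Patients are to notify the investigator if they became pregnant "either during the treatment phase of the study or within 30 days or five half-lives after the treatment period, whichever is longer". For the time on study, Section 3.1.13 says: "Should a female patient become pregnant or suspect she is pregnant while participating in this study, she should inform her treating physician immediately". Under Maternal exposure, Section 7.2.6.2 adds: "If any pregnancy occurs in the course of the study, then the Investigator or other site personnel should inform the appropriate AstraZeneca representatives", within 24 hours. It also says that pregnancy outcomes "should be followed up and documented even if the patient was discontinued from the study".

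**The concern.** Outcomes of partner pregnancies are collected to learn what happens when conception takes place while the father is exposed. As worded, the rule asks for the pregnancies that begin after the protected period and passes over those that begin within it.

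Section 11.7 requires the study to be conducted as the protocol describes. Section 7.2.6.2 also makes site staff obtain the partner's consent before collecting pregnancy information. Staff therefore need a window they can apply, and the literal one would send them to the wrong pregnancies. What is at stake is a small piece of safety information. Sample size, error rates and efficacy analyses are unaffected.

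**Working it through.** The plan states no figure to reproduce. The check is a comparison of passages plus calendar arithmetic, with the first dose as day 0.

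**Inputs**
- Combination dosing: Day 1 of four 28-day cycles (Section 4.2). The last combination dose is at 3 × 28 = day 84.
- Monotherapy: every 2 weeks from week 16, up to 18 doses (Section 8.3). The last dose is at week 16 + 2 × 17 = 50, which is day 350 if there are no delays.
- Protected period: the later of last combination dose + 180 days and last monotherapy dose + 90 days (Section 7.2.6.2).

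**Protected period against the literal follow-up window**

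| Patient | Protected period ends | Partner follow-up starts, read literally | Protected days covered |
|---|---|---|---|
| Stops after 4 combination doses | 84 + 180 = day 264 | day 264 | 0 of 264 |
| Completes 18 monotherapy doses | later of 264 and 350 + 90 = day 440 | day 440 | 0 of 440 |

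The two windows meet end to end and do not overlap. The result does not depend on how long treatment lasts, because both are measured from the same last dose.

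**Is a partner window set elsewhere?** Not clearly.
- The 24-hour notification and outcome rules sit under Maternal exposure, and the outcome rule is framed around the patient.
- Section 7.2.4 concerns patients who become pregnant.
- Routine adverse-event collection does not clearly reach a partner pregnancy, because Section 7.2.6.2 says it is not an adverse event.

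**Which period should the rule cite?** For the full-course patient, Sections 4.5.1 and 7.2.6.2 end protection at day 440. Section 3.1.13 ends it at 350 + 180 = day 530. The protocol disagrees with itself by 90 days.

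**Section 7.2.4 window.** This runs to the longer of 30 days or five half-lives (5 × h) after treatment. It is shorter than 180 days only if h < 180/5 = 36 days, and shorter than 90 days only if h < 90/5 = 18 days. The documents give no half-life, so the values below are assumptions that only show how the answer moves.

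| Assumed h (days) | Window (days) | Short of 180 | Short of 90 |
|---|---|---|---|
| 10 | 50 | 130 | 40 |
| 20 | 100 | 80 | 0 |
| 30 | 150 | 30 | 0 |
| 36 | 180 | 0 | 0 |

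The comparator also changes. The 180 days in Section 4.5.1 run from the last combination dose. For a patient who completes maintenance they expire at day 264, before treatment ends, so under that section the 90-day limit governs.

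**The case against.** **The sentence is garbled rather than a deliberate rule.** It lacks an auxiliary verb, and its starting point has no matching end, so words have probably been lost. The paragraph above it states the protected period, and a sensible reader can recover the intent. That stands as to cause: this should be read as a probable drafting slip, not a design decision. The source file should be checked in case the words were lost in conversion. If the slip is in the source, it is still the instruction that sites follow.

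**The maternal rules speak of any or all pregnancies and might be stretched to partners.** They might, but their heading and wording concern the patient, and the partner paragraph sets its own, different window.

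**The practical effect is small.** This stands. Only male patients with partners who can become pregnant are concerned, and Appendix E records that the study closed on 7.20.2020 for low accrual.

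**A reader might infer that female patients need report pregnancies only up to 30 days or five half-lives, leaving a known gap before day 180.** The documents do not support this. Section 7.2.4 includes the treatment phase, takes the longer of its two limits, and concerns pregnancies identified after study completion. Sections 3.1.13 and 7.2.6.2 (Maternal exposure) already cover patient pregnancies during the study, and Section 4.7 plans follow-up for 3 years. Without a half-life, neither the existence nor the size of a gap can be shown. What remains is that the Section 7.2.4 window is not tied to the contraception period and cannot be calculated from the protocol. How long a patient counts as on study is also uncertain, because Section 4.8 ends study observation when another anticancer therapy starts.

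**Conclusion.** The point holds for partner pregnancies. The follow-up sentence in Section 7.2.6.2 is wrong as written: taken literally it covers none of the protected period (0 of 264 or 0 of 440 days in the two cases worked). This assumes that the sentence reads the same in the source protocol and that doses are given on schedule; the lack of overlap does not depend on the schedule. The consequence is minor. It is an editorial error in a safety-collection rule that affects few patients and no analysis.

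For patient pregnancies only a secondary point holds: the Section 7.2.4 window should be reconciled with the contraception period. No shortfall is claimed.

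**What to change.** 1. Reconcile the contraception period after monotherapy between Section 3.1.13 (180 days) and Sections 4.5.1 and 7.2.6.2 (90 days). The duration is for the sponsor and investigator to settle.
2. Reword the partner sentence in Section 7.2.6.2 to say that the outcome of any partner pregnancy occurring from the patient's first dose to the end of the reconciled contraception period should, if possible, be followed up and documented. Citing the period by section number keeps the rule aligned if the duration changes.
3. Reconcile the post-study notification window in Section 7.2.4 with that same period, or state how the two relate.

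The cost is a few wording changes in one amendment, with no new visit, test or analysis.
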